5.1.2 Additional treatment

Antipyretic will be allowed for symptomatic management of fever (see [Section 5.5.7](#)). No other additional treatment beyond investigational drug and control drug are included in this trial. The control drug, Coartem, will be also provided as rescue medication ([Section 5.5.6](#)).

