5.5.7 Prior and concomitant medication

Prior medications are defined as drugs taken and stopped prior to first dose of study medication.

Concomitant medication is defined as any medication, other than the Investigational Medicinal Product (IMP), which is given at least once between the day of first dose of randomized study medication and the last day of study visit (including those which were started pre-baseline and continued into the treatment period), including prescription and over-the-counter medicines, and any traditional or herbal remedies.

Paracetamol as an antipyretic, and metopimazine for repeated vomiting (or if not available, any other antiemetic which is not known to prolong QT and/or cause torsade de pointes) will be allowed. If paracetamol or equivalent drug is given as an antipyretic up to 72 hours prior first dose, it has to be reported as prior medication

Metoclopramide is contraindicated from the period prior to first dose to Day 5 post-dose (120 hours).

Beta-lactam antibiotics can be given in case of a bacterial infection appearing after enrolment. All other antibiotics, new-quinolones included, should be avoided where possible.

The investigator must instruct the patient to notify the study site about any new medications he/she takes after the patient was enrolled into the study. All medications, procedures and significant non-drug therapies (including herbal therapy, physical therapy and blood transfusions) administered after the patient was enrolled into the study must be recorded in the concomitant medications eCRF.

Each concomitant drug must be individually assessed against all exclusion criteria/prohibited medication. If in doubt the investigator should contact the Novartis medical monitor before randomizing a patient or allowing a new medication to be started.

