5.5.8 Prohibited medication

Use of the following treatments is NOT allowed as per below recommendation in **KAE609 Cohorts**:

- Antimalarials other than the study drug and rescue medication (Coartem) are not permitted during the entire study period.
- Herbal medication should not have been taken within 1 week before the study treatment is given and should be avoided until the last study visit.
- Any other investigational treatment for the whole study duration.
- KAE609 undergoes CYP3A4 metabolism thus potent and moderate CYP3A inhibitors (such as HIV antivirals: e.g., ritonavir miscellaneous: e.g., clarithromycin, itraconazole, ketoconazole, grapefruit juice, verapamil, cimetidine) and inducers (such as HIV antivirals: e.g., efavirenz miscellaneous: e.g., barbiturates, carbamazepine, phenytoin, rifampin, St. John's wort) are not allowed up to 14 days before enrolment in the study or minimum 5 half-lives of the perpetrator drug (whichever is longer) administration and up to 7 days post administration.
- KAE609 is a potent inhibitor of CYP2C19 and can potentially increase the exposure of drugs which are a substrate of CYP2C19 by many folds (such as Proton pump inhibitors: e.g., lansoprazole, omeprazole, anti-epileptics: e.g., phenytoin, miscellaneous: e.g., amitriptyline, chloramphenicol, clomipramine, indomethacin, nelfinavir, progesterone (synthetic progestins used in hormonal contraceptives are not prohibited since they are metabolized by CYP3A4), proguanil, propranolol, warfarin). Therefore, these are prohibited for the treatment duration and 7 days after last dose.
- Drug known to cause QTc prolongation or known to be potentially hepatotoxic (see [Appendix 4](#)) are prohibited for the treatment duration and 7 days after last dose.

Apart from the above mentioned possible interactions in vitro data suggest KAE609 is inhibitor of CYP2B6, CYP2C9, CYP2A6, CYP1A2, CYP2D6, CYP2C8, and CYP3A4, however, assessment including SimCYP simulation suggests that potential change in the exposure of drug substrate of any of these would be less than two fold and unlikely to be of clinical significance. Nonetheless caution should be exercised such as staggering the dose of victim drug by ~12 hours from last dose of KAE609.

Use of the following treatments is NOT allowed as per below recommendation in **Coartem/Riamet Cohorts**:

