Coartem/Riamet prescribing information should be followed in general. Use of any prescription drugs (with particular attention to use of CYP3A4 inhibitors, e.g., erythromycin, ketoconazole, itraconazole, cimetidine or CYP3A4 inducers e.g., rifampin, phenobarbital etc. Also drugs metabolized by CYP2D6 like flecainide, metoprolol, imipramine, amitriptyline, clomipramine, neuroleptics and those that increase QTc interval like terfenadine, astemizole, cisapride) is prohibited during study and within four (4) weeks prior to dosing. Herbal supplements are also prohibited during study and within one week prior to dosing. Medication which may be required to treat adverse events can be administered considering the potential interaction. Administration of paracetamol (daily total dose not to exceed 3g) / acetaminophen is acceptable, but dose and time of administration must be documented in the Concomitant medications / significant non-drug therapies section of the eCRF.

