Acute Kidney Injury: Serum creatinine increase \geq 50% compared to baseline	Follow up within 24-48h if possible Consider study treatment discontinuation Consider patient hospitalization /specialized treatment
Urine Event	
New dipstick proteinuria \geq 1+ Albumin- or Protein-creatinine ratio increase \geq 2-fold Albumin-creatinine ratio (ACR) \geq 30 mg/g or \geq 3 mg/mmol; Protein-creatinine ratio (PCR) \geq 150 mg/g or $>$ 15 mg/mmol	Confirm value after 24-48h Perform urine microscopy Consider study treatment discontinuation
New dipstick glycosuria \geq 1+ not due to diabetes	Blood glucose (fasting) Perform serum creatinine
New dipstick hematuria \geq 1+ not due to trauma	Urine sediment microscopy Perform serum creatinine
For all renal events:	

Document contributing factors in the CRF: co-medication, other co-morbid conditions, and additional diagnostic procedures performed
 
Monitor patient regularly (frequency at investigator's discretion) until either:
 
Event resolution: sCr within 10% of baseline or protein-creatinine ratio within 50% of baseline, or
 
Event stabilization: sCr level with \pm 10% variability over last 6 months or protein-creatinine ratio stabilization at a new level with \pm 50% variability over last 6 months.
 
sCr: serum creatinine.
	

16 Appendix 4: Medications, herbs and toxins as cause of ALT/AST elevations

Table 16-1 Medications, herbs and toxins as cause of ALT/AST elevations

Medications and drugs	Herbs and alternative medications
Alpha-methyldopa	Chaparral leaf
Amoxicillin-clavulanic acid	Ephedra
Amiodarone	Gentian
Bosentan	Germander
Carbamazepine	Ji Bu Huan
Dantrolene	Senna
Disulfiram	Kava kava
Etretinate	Scutellaria (skullcap)
Fluconazole	Shark cartilage
Glyburide	Vitamin A
Halothane	Illicit drugs
Heparin	Anabolic steroids
HMG-Co A reductase inhibitors	Cocaine
Isoniazid	Ecstasy (MDMA)
Ketoconazole	Phencyclidine (PCP)
Labetalol	Toxins
Nicotinic Acid	Carbon tetrachloride
Nitrofurantoin	Chloroform
NSAIDs	Dimethylformamide
Phenylbutazone	Hydrazine
Phenytoin	Hydrochlorofluorocarbons
Propylthiouracil	2-Nitropropane
Protease inhibitors	Trichloroethylene
Sulfonamides	Toluene
Terbinafine	
Trazadone	
Troglitazone (withdrawn)	
Valproic Acid

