#### **2.4.2 Prior, concomitant and post therapies**

Prior and concomitant medications will be summarized in separate tables by cohort and treatment group.

Concomitant rescue and other anti-malarial medications will also be summarized by cohort and treatment group.

Note – The only rescue medication considered in this study is Coartem. All other antimalarial drugs are prohibited and if taken then it will be considered as PD. If Coartem is used after discontinuation of study drug due to early treatment failure, late clinical failure or late parasitological failure then it should be considered as rescue medication,. Rescue medication will be captured along with other concomitant medications by the investigators under rescue medication category.

Any patient on KAE609 who does not need rescue medication up to Study Day 28 will be given Coartem as post therapy at the end of the study (Study Day 29) and will be followed as per standard medical care. Prior medications are defined as drugs taken and stopped prior to first dose of study medication. Any medication given at least once between the day of first dose of study medication and the last day of study visit will be a concomitant medication, including those which were started pre-baseline and continued into the treatment period.

Prior and concomitant medications will be coded according to the latest version of WHO Drug Reference List dictionary which employs the ATC. The number and percentage of patients taking prior and concomitant medications will be summarized for each cohort and treatment by ATC class and preferred term (PT).

Number and percentage of the patients receiving prohibited prior and concomitant drugs will be summarized. Details regarding prohibited drugs are mentioned in [Table 5-9](#). PK related prohibited medications (the drugs which are prohibited only within first 7 days from first dose) and non-PK related prohibited medications will be summarized separately.

Safety set will be used.

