Acetaminophen	N02BE01	paracetamol	Paracetamol=acetaminophen code not available for the following: Amoxicillin-clavulanic acid (co- amoxiclav) , Flucanazole, Glyburide, Ecstasy (MDMA) , Phencyclidine, Labetolol, Hydrazine, Trazadone, Ephedra
Alpha-methyldopa	C02AB	Methyldopa	
Ephedra	C01BD01	amiodarone	
Amoxicillin-clavulanic acid	A06AB06	senna glycosides	
Amiodarone	M03CA01	dantrolene	
Senna	N07BB01	disulfiram	
Dantrolene	P03AA04	disulfiram	
Disulfiram	A11CA	Vitamin A, plain	
Vitamin A	N01AB01	halothane	
Glyburide	A14A	ANABOLIC STEROIDS	
Halothane	B01AB01	heparin	
Anabolic steroids	C05BA03	heparin	
Heparin	S01XA14	heparin	
Cocaine	N01BC01	cocaine	
HMG-Co A reductase inhibitors	R02AD03	cocaine	
	S01HA01	cocaine	
Isoniazid	S02DA02	cocaine	
Phencyclidine (PCP)	C10AA	HMG CoA reductase inhibitors	
Ketoconazole	J04AC01	isoniazid	
Labetolol	D01AC08	ketoconazole	

Carbon tetrachloride	G01AF11	ketoconazole
	J02AB02	ketoconazole
Nicotinic Acid Chloroform	C04AC01	nicotinic acid
	C10AD02	nicotinic acid
Nitrofurantoin	J01XE01	nitrofurantoin
NSAIDs	M01A	NSAID
Hydrazine	M01AA01	phenylbutazone
Phenylbutazone	N03AB02	phenytoin
Phenytoin	J05AE	Protease inhibitors
Protease inhibitors	A07AB	Sulfonamides
Sulfonamides	D06BA	Sulfonamides
Terbinafine	G01AE	Sulfonamides
Trazadone	S01AB	Sulfonamides
Troglitazone	D01AE15	terbinafine
(withdrawn)	D01BA02	terbinafine
Valproic Acid	A10BG01	troglitazone
Bosentan	N03AG01	valproic acid
Propylthiouracil	C02KX01	bosentan
	D05BB01	etretinate
	H03BA02	propylthiouracil
	N01AB02	chloroform
	N01AB05	trichloroethylene

The prohibited medications listed in [Table 5-8](#) is not an exhausted list. Concomitant medications not listed above will be manually checked and will be categorized as Prohibited medication or non-prohibited medication.

The final list with all prohibited medications that were determined by medical review before database lock can be found in the excel file 'Copy of CKAE609A2202\_possible\_prohibited medications.xlsx'.

Copy of  
CKAE609A2202\_poss

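### Paracetamol is permitted in all arms, but its 3 g/day maximum and dose-and-time record are written only for Coartem patients, and SAP Table 5-8 lists it as prohibited

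*Protocol*

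**What the plan says.** Protocol 5.1.2 gives a general permission, "Antipyretic will be allowed for symptomatic management of fever", and points to 5.5.7. Section 5.5.7 names the drug among the allowed treatments: "Paracetamol as an antipyretic, and metopimazine for repeated vomiting". Neither section distinguishes arms or states a dose. Section 5.5.7 also requires paracetamol taken for fever in the 72 hours before first dose to be reported, and all medication after enrolment to be entered in the eCRF, whatever the arm.

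Protocol 5.5.8 has two blocks. The KAE609 block does not name paracetamol. For the treatment period plus 7 days it bars any "Drug known to cause QTc prolongation or known to be potentially hepatotoxic", with a reference to Appendix 4 ("Medications, herbs and toxins as cause of ALT/AST elevations"). The Coartem/Riamet block bars prescription drugs and then adds: "Administration of paracetamol (daily total dose not to exceed 3g) / acetaminophen is acceptable, but dose and time of administration must be documented".

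SAP 5.2, Table 5-8, is the table of prohibited medications by ATC code. It includes acetaminophen, N02BE01, with a comment beginning "Paracetamol=acetaminophen code not available for the following". The note after the table adds: "The final list with all prohibited medications that were determined by medical review before database lock can be found in the excel file". SAP 2.4.2 uses the classification descriptively: "Number and percentage of the patients receiving prohibited prior and concomitant drugs will be summarized".

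**The concern.** The same antipyretic has three written statuses: allowed up to 3 g/day (Coartem), allowed with no stated maximum (KAE609), and prohibited (SAP Table 5-8).

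This matters because of what the trial measures. The primary endpoint is a rise of at least 2 CTCAE grades in ALT or AST, and the same event in 2 patients (Cohorts 1 and 2) or 3 patients (Cohorts 3 to 6) suspends recruitment. Protocol 3.2 includes Coartem to help tell whether hepatic events belong to KAE609 or to malaria. Protocol 7.3 asks for causality of liver events to be judged by excluding alternatives, and names co-medication as one. The SAP itself places paracetamol among drugs taken from Appendix 4, the list of causes of transaminase rises. A rule on such a drug should read the same in every arm, and the arms with suspected hepatotoxicity are the last that should lack a stated limit.

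On the SAP side, a permitted antipyretic in a febrile population could be counted as prohibited medication.

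**Working it through.** The plan gives no figure for this point, so the check is mainly a comparison of texts.

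**1. Where each rule applies**

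| Source | Arms | Status of paracetamol | Maximum | Recording |
|---|---|---|---|---|
| Protocol 5.1.2, 5.5.7 | all | allowed for fever | none | eCRF entry; dose and time not spelled out |
| Protocol 5.5.8, KAE609 block | KAE609 | not named | none | not mentioned |
| Protocol 5.5.8, Coartem block | Coartem | allowed | 3 g/day | dose and time explicit |
| Protocol Appendix 4 | KAE609, by reference | not listed | – | – |
| SAP Table 5-8 | not stated | prohibited | – | – |

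**2. Does the KAE609 ban on hepatotoxic drugs supply a limit?** No. It works through Appendix 4, which does not list paracetamol, and 5.5.7 allows the drug by name. The specific permission governs, and it has no maximum.

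**3. Is the SAP row qualified?** Not within the table. A comment on the antimalarial rows records that artemether and artemether/lumefantrine were deliberately left out; no such exception is noted for paracetamol. The manual check described after the table covers medications that are not listed, and paracetamol is listed. Only the separate final list could remove it.

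**4. What does the row feed?** The count in SAP 2.4.2. It does not touch the primary analysis, which uses the safety set. In SAP Table 5-9 that set is defined by membership of the randomized set and intake of study drug. The same table excludes patients from the per-protocol or PK set for prohibited medication only where exposure was found to change.

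**5. How many patients are in each group of arms?** From the planned arm sizes:
- KAE609: 3 arms × 10 + 6 arms × 20 = 30 + 120 = 150.
- Coartem: 6 cohorts × 10 = 60.
- Total: 150 + 60 = 210, which matches the protocol. Shares: 150/210 = 71.4% and 60/210 = 28.6%.

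**6. How much of the risk period is supervised?** The first two escalation criteria in Protocol Table 3-1 use Day 1 to Day 15, which is 15 days. Inpatient care runs from Day 1 to Day 4, which is 4 days, leaving 15 − 4 = 11 outpatient days. Patients should have cleared fever before discharge, so antipyretic use should be lower in those 11 days.

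**The case against.** The strongest reply is structural. The Coartem block bans prescription drugs, so it had to make an exception for paracetamol; the KAE609 block has no such ban, so the permission in 5.5.7 was enough. This stands as the reason the drug is mentioned in one block only. It does not explain why the maximum was not put in 5.5.7.

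It can also be said that the KAE609 arms are the more protected ones. Only their block bars hepatotoxic drugs expressly. Section 5.5.7 allows paracetamol only as an antipyretic, has every concomitant drug assessed against the prohibited list, and sends doubtful cases to the medical monitor. The safety review committee receives concomitant medication together with the ALT/AST output (SAP Table 2-6). All of this stands, and it limits the practical effect.

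A reader might infer more than the documents support:
- *That KAE609 paracetamol use goes unrecorded.* It does not: 5.5.7 requires eCRF entry in every arm. What is missing is the explicit demand for dose and time, and the documents do not show that these would be absent.
- *That the comparison with pooled Coartem is biased.* The documents give no frequency of use above 3 g/day and no associated rate of ALT/AST rise, so no bias is shown.
- *That 71% of patients are affected.* That is the share in arms without a written maximum, not the share exceeding it.
- *That the SAP certainly miscounts.* The final list was set by medical review and may already omit the row.

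**Conclusion.** The inconsistency is real and minor. The protocol writes a maximum and an explicit dose-and-time record for the reference arm only, without a reason for withholding them from KAE609. SAP Table 5-8, read alone, contradicts the protocol's permission.

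The effect cannot be quantified from the documents and is probably small, given the recording rule in all arms, the inpatient period and the fever criterion for discharge. No primary result changes. If the row survived on the final list, the consequence is an inflated descriptive count of prohibited medication.

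The conclusion rests on two assumptions: that Appendix 4 as provided is complete, and that no other study document sets a paracetamol limit for KAE609 patients. The SAP part also depends on the content of a file that is not available. The wording does not show that different paracetamol exposure by arm was intended; a drafting gap is the simpler explanation.

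**What to change.** 1. **Protocol 5.5.7:** state the 3 g/day maximum and the dose-and-time record for all arms. Keep a cross-reference in the Coartem block of 5.5.8, which would otherwise bar the drug. Protocol 11.1 requires a written amendment with the usual approvals, so include this with the next one.
2. **SAP Table 5-8:** delete the paracetamol row and confirm that it is off the final list. Deletion is better than flagging only use above 3 g/day, because a table of ATC codes has no dose field and such a flag would need a daily-dose derivation with rules for missing doses.
3. **Listing:** show paracetamol dose and timing beside each primary ALT/AST event, from the concomitant-medication data already collected. Any missing dose or time would then be visible.

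The cost is a small amendment, one deleted row, one listing and slightly more recording in the KAE609 arms. The SAP history has an entry made after database lock, so for patients already in the data only steps 2 and 3 can still help.

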5.5.9 Emergency breaking of assigned treatment code

Emergency breaking of assigned treatment code is not needed since this is an open-label trial.

5.6 Study completion and discontinuation

5.6.1 Study completion and post-study treatment

Each patient will be required to complete the study in its entirety and thereafter no further study treatment will be made available to them.

A patient will be considered to have completed the study when the patient has completed the last visit planned in the protocol, and any repeat assessments associated with this visit have been documented and followed-up appropriately by the investigator.

Patients who discontinue study drug and/or are put on rescue medication at any time during the study will be followed for the entire study duration (i.e., until Study Day 29).

The investigator and/or referring physician must provide follow-up medical care for all patients who are prematurely withdrawn from the study, or must refer them for appropriate ongoing care. This care may include:

- Treatment of their malaria and complications
- Treatment of secondary infections
- Treatment of associated diseases

A safety review committee will review patient safety at several time points (see [Section 8.4](#)) and may recommend stopping a treatment arm or the study early for safety reasons.

5.6.2 Discontinuation of study treatment

Patients will be treated under hospital supervision during the treatment period. Discontinuation of study treatment for a patient occurs when study drug is stopped earlier than the protocol planned duration, and discontinuation can be initiated by either the patient or the investigator. For patients assigned to 1-day treatment arm, they will not be considered as treatment discontinuation if those discontinuation events occur after they have completed the treatment as assigned.

The investigator must discontinue study treatment for a given patient if, on balance, he/she believes that continuation would negatively impact the participation of the patient in the trial.

Study treatment must be discontinued under the following circumstances:

- Patient request
- Pregnancy (see [Section 6.5.6](#) and [Section 7.6](#))
- Use of prohibited treatment as per recommendations in [Section 5.5.8](#)
- Any situation in which study participation might result in a safety risk to the patient and/or any adverse events that in the judgment of the investigator, taking into account the patient's overall status, prevent the patient from continuing participation in the study
- Unsatisfactory therapeutic effect (see [Section 6.5.8](#))

- Emergence of the following adverse events: severe nausea/vomiting, severe pruritus, increases in QTcF to >500 ms (based on repeat Electrocardiograms (ECGs), development of ventricular arrhythmia or clinically significant (symptomatic) bradycardia (see [Appendix 3](#))
- Any laboratory abnormalities (e.g., LFT increase) that in the judgment of the investigator, taking into consideration the patient's overall status, prevent the patient from continuing taking the study medication (see [Appendix 2](#))
- Deviation from the planned dose regimen for the study drug

Patients who discontinue study drug for any of the above reasons may be given rescue medication at the discretion of the investigator and will be followed for the whole study duration until Study Day 29.

If discontinuation of study treatment occurs, the patient should NOT be considered withdrawn from the study and should undergo the scheduled study visits. The investigator must determine the primary reason for the patient's premature discontinuation of study treatment and record this information on the Treatment Completion eCRF. If the patient completes all the scheduled visits in the treatment period, the patient is considered to have completed the treatment period. If a patient does not complete the scheduled visits in the treatment period, premature treatment discontinuation visit assessments detailed in the assessment schedule table should be completed and recorded in the eCRF. The only reason a patient would not complete all these visits is because he/she withdrew study consent/ died/ lost to follow up or the sponsor terminated the study early.

If the patient cannot or is unwilling to attend any visit(s), the site staff should maintain regular telephone contact with the patient, or with a person pre-designated by the patient, to collect key safety data. This telephone contact should preferably be done according to the study visits schedule.

The investigator must also contact the IRT to register the patient's discontinuation from study treatment (this patient will not be replaced).

